#### 3.7 Patient Allocation to study groups

There is generally one patient per room and patient assignment to a room is largely driven by unit census (i.e., bed availability) as well as other clinical factors: e.g., need for an isolation room, nursing availability. All of these factors vary independently of the preferences of the patient or research team, reducing the risk for systematic bias. The unit of randomization is by pod on a floor. Research coordinators as part of the "on-boarding process" will also provide culturally competent instructions and in-person teaching for device use.

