#### 3.10 Statistical Analysis Plan

Means with standard deviations, frequencies and percentages will be used to convey descriptive statistics. Standard tests of association (chi-squared, t-tests) will be used for comparing characteristics between the control and intervention arm. Inverse probability weighting using propensity scores modeled from baseline covariates and instrumental variable analysis will be the quasi-experimental approach used to minimize any confounding bias from our pseudorandomization process. We will model most outcomes with weighted multivariate generalized mixed effects regression models, focusing primarily on estimate the average treatment effect. The effect of unit will be modeled using a random intercept term. Care utilization outcomes will be compared using standard time-to-event models and log-rank testing. Final analyses will be performed when all data has been entered, cleaned, and locked.

All analyses will be based on an intent-to-treat framework. For missing covariate values, a multiple imputation approach will be used. Outcomes will be assumed to be missing at random; a sensitivity analysis will be conducted to assess the robustness of significant findings to different magnitudes of missing data mechanisms.

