#### 4.3 Research Plan

- a. *Study Population:* In order to participate in the sub-study, participants must be enrolled in the PROSPER trial. We plan to enroll 100 participants from the parent trial in this pilot study, 50 participants from each arm of the parent trial. The inclusion and exclusion criteria for the sub-study are the same as the parent trial.
- b. *Inclusion criteria:* Adult patients (> 18 years of age), English-speaking and able to complete consent and survey materials are eligible to participate. Potential participants must be admitted to the hospital for an anticipated minimum of 3 nights.
- c. *Exclusion criteria:* Vulnerable populations (pregnant, incarcerated, history of delirium, suicidal ideation, ischemic stroke with measurable neurologic deficit, cerebral palsy, seizures), primary brain tumor/metastases patients) are not eligible. Patients concurrently enrolled in contact isolation with SARS-CoV2 will be excluded. Lastly, hospice or hospice-bound patients will also be excluded. Any patient can remove themselves from the study at any point.

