#### 4.4 Study Methods

- a. Study design: The pilot sub-study will be integrated into the parent trial. This pilot study leverages a twogroup, pre-post test design to conduct preliminary tests for differences between the experimental arm (PROSPER intervention with digital vital sign monitoring) and the control arm (PROSPER intervention without digital vital sign monitoring) on objective sleep parameters and patient reported sleep disturbances and fatigue.
- b. Recruitment: Once participants are enrolled in the parent trial, they will be evaluated for inclusion in the pilot sub-study based on the availability of the device that measures objective sleep parameters (Actiwatch Spectrum Pro®). Thirty wrist actigraphy devices (Actiwatch Spectrum Pro®) are available for use at any given time. Fifty participants from the patient care units designated as the intervention arm for the parent trial will be enrolled as treatment patients in the substudy; fifty participants from the patient care units designated as the control arm will be enrolled as control patients in the substudy. Participants will be consecutively enrolled in the sub-study as they are enrolled in the parent study although enrollment may pause if wrist actigraphy devices are not available.
- c. Instrumentation: Objective sleep parameters will be assessed with the Actiwatch Spectrum Pro® during the course of hospitalization, consistent with the parent trial. Patient-reported sleep disturbances will be measured with the PROMIS Sleep Disturbance Adult Short Form. Patient-reported fatigue will be measured in real-time with a one-time global fatigue intensity rating over the course of the hospitalization and the PROMIS Fatigue Adult Short Form. The PROMIS instruments will be completed upon enrollment and discharge +/- 1 day, consistent with the parent trial.

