#### a. Primary Objective

For each variable, differences between PROSPER with digital vital sign monitoring (the experimental group) and PROSPER without digital vital sign monitoring (the control group) will be calculated and reported with 95% twosided confidence intervals. Further exploratory analysis with ANCOVA models will incorporate covariates of baseline measures and length of stay to assess the relative efficiency gain of each covariate, as well as potential for confounding.

Based on previous work by the investigators, the confidence interval for the difference between groups should have expected lengths of no more than 54 (total sleep time, min), 12 (sleep latency, min), 5 (sleep efficiency, %), 17 (frequency and duration of awakenings after sleep onset, min), and 5 (number of awakenings).

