#### b. Secondary Objective

Descriptive data will be computed for the real-time fatigue scores, PROMIS Fatigue, and PROMIS Sleep disturbance. Preliminary analysis will be conducted using a two-sided independent samples *t*-tests comparing PROSPER with digital vital sign monitoring (experimental group) compared to PROSPER without digital vital sign monitoring (control group) over the course of the hospitalization.

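### The sub-study analysis takes 100 patients as independent although care unit defines arm, so its 95% intervals and 5% tests are miscalibrated if outcomes vary between units within a service

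*Combined protocol and SAP*

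**What the plan says.** Section 3.4 assigns arm by location. On the P10 floor, unit A is intervention and unit B is control for the colorectal service; G21 is intervention and G22 is control for the hospitalist service. Section 3.7 states: "The unit of randomization is by pod on a floor". The sub-study takes "50 participants from each arm of the parent trial" (4.3), and its recruitment paragraph (4.4 Study Methods, b) draws each group from the units that define the arm: "Fifty participants from the patient care units designated as the intervention arm for the parent trial will be enrolled as treatment patients in the substudy".

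For the parent trial, section 3.10 says: "The effect of unit will be modeled using a random intercept term". Section 4.5 has its own analysis text and does not carry this over:

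- **4.5a (primary):** a between-group difference for each sleep variable, with intervals that "will be calculated and reported with 95% twosided confidence intervals". An exploratory ANCOVA adds baseline measures and length of stay only.
- **4.5a (precision):** from earlier work by the investigators, "the confidence interval for the difference between groups should have expected lengths of no more than 54" minutes for total sleep time, then 12 (latency, min), 5 (efficiency, %), 17 (WASO, min) and 5 (number of awakenings). No SD, ICC or clustering allowance is given.
- **4.5b (secondary):** "two-sided independent samples *t*-tests" for fatigue and sleep disturbance.

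**The concern.** When whole units are assigned to arms, any difference between units that is not due to the device goes straight into the arm difference. An interval built only from patient-to-patient variation does not include that component. The protocol itself treats the inpatient environment as a determinant of sleep: its background section lists noise, bedtime medication, early phlebotomy and lighting as targets of the bundle. Both arms receive the bundle, which may narrow differences between units, but nothing in the documents shows that it removes them, and 3.10 plans for a unit effect in the parent trial.

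The planned product of the primary objective is an estimate with an interval for each sleep measure. If the interval covers less than its label says, a ward difference can be read as a preliminary device effect with more precision than the design supports, and carried into the planning of a later trial.

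**Working it through.** **Inputs from the documents.** 50 patients per arm (4.3); at most four units, two per arm, one per service in each arm (3.4); two-sided 95% intervals and lengths 54, 12, 5, 17, 5 (4.5a).

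**Assumptions, because the documents are silent.** 25 patients per unit; within-service unit ICC of 0.01, 0.02 or 0.05; normal outcomes; no device effect.

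**Step 1: the plan's own lengths.** For independent patients, L = 2 × t(0.975, 98) × SD × √(2/50) = 2 × 1.984 × SD × 0.2 = 0.794 × SD. With no SD given, the lengths cannot be reproduced; the formula can only be solved backwards. For total sleep time, 54 / 0.794 gives an SD of about 68 min. The others imply about 15.1 min, 6.3%, 21.4 min and 6.3 awakenings. So 54 min matches an independence interval with SD about 68 min. Whether that SD contains slack cannot be determined.

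**Step 2: variance inflation.** Design effect = 1 + (m − 1) × ICC, with m = 25. Lengths are multiplied by its square root, keeping the same critical value.

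| ICC | Design effect | Multiplier | Total sleep time (min) | Latency (min) | Efficiency (%) | WASO (min) | Awakenings |
|---|---|---|---|---|---|---|---|
| 0 | 1.00 | 1.000 | 54 | 12 | 5 | 17 | 5 |
| 0.01 | 1.24 | 1.114 | 60.1 | 13.4 | 5.6 | 18.9 | 5.6 |
| 0.02 | 1.48 | 1.217 | 65.7 | 14.6 | 6.1 | 20.7 | 6.1 |
| 0.05 | 2.20 | 1.483 | 80.1 | 17.8 | 7.4 | 25.2 | 7.4 |

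**Step 3: coverage of the planned simple interval.** By approximation, coverage = 2Φ(1.984 / multiplier) − 1, which gives 92.5%, 89.7% and 81.9%. Simulation (20,000 sub-studies per ICC, four units of 25) gives 95.0% at ICC 0, then 92.3%, 89.1% and 81.0%. For the t-tests in 4.5b, the same settings give false-positive rates of about 8%, 11% and 19%. The simple interval's mean length barely moves: with SD 68 min it is 53.8 min at ICC 0 and 53.2 min at ICC 0.05. Coverage falls; length does not.

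**Step 4: sensitivity to the assumptions.**

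- *Variance due to service.* Each service has one unit in each arm, so service differences cancel when the service mix is equal across arms. At a total between-unit ICC of 0.05, the false-positive rate is about 19% if none of the variance is due to service, 12% if half is, 7.7% if 80% is, and 5% if all is.
- *Unequal units.* With 40 and 10 patients in each arm's two units, the size-weighted m is (40² + 10²) / 50 = 34. The multiplier at ICC 0.05 is √(1 + 33 × 0.05) = 1.63, and the false-positive rate is about 23% (coverage about 77%).
- *One service only.* Section 4.4 sets no quota by service. With one unit per arm, m = 50, and the false-positive rate is about 11% at ICC 0.01 and 30% at ICC 0.05.

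**Step 5: can the unit variance be estimated?** Four units minus two arms leaves 2 unit-level degrees of freedom (t = 4.303). With service also fixed, 1 remains (t = 12.7). Even with 2, the total sleep time interval at ICC 0.01 would be 54 × 1.114 × 4.303 / 1.984, about 130 min. A random intercept fitted to the sub-study would therefore be uninformative.

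**The case against.** Four arguments on the other side have force.

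**Nothing shows that the ICC exceeds zero.** Correct: at zero the problem vanishes. A reader might infer that the intervals are certainly too narrow; the documents do not establish that, and the point is conditional. What stands is that 3.10 plans for a unit effect and 4.5 does not.

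**The stated lengths may be sound.** A reader might infer that 54 min and the other limits are wrong, or are not upper limits. That is not supported. They are expected lengths for the planned interval, whose mean length stays below 54 min in the simulation with SD 68 min. Only a different, wider interval exceeds them, and with no SD given slack cannot be excluded. The fair criticism is that they mention no allowance for unit.

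**81% is not an estimate.** It applies only if the within-service ICC is 0.05 with equal units. Taking it as the expected coverage would overstate what is known: the pairing of units within service removes part of the between-unit variance when the mix is balanced.

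**This is a pilot.** It looks for preliminary effects and trends, plans no hypothesis test for the primary objective, and has no decision rule. That lowers the consequence, but an interval labelled 95% should still say what it covers.

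Also, only the t-tests are named as independent-samples. For the primary intervals, independence is inferred from the absence of any unit term and from the ANCOVA covariates; no other method is stated.

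**Conclusion.** The point holds in conditional form. Section 4.5 analyses unit-assigned patients as independent, while the parent plan for the same units does not. If sleep or fatigue varies between units within a service, the nominal 95% intervals and 5% tests are miscalibrated. Under the working assumptions (25 per unit, within-service ICC 0.01 to 0.05), coverage runs from about 92% down to 81%: closer to 95% where service explains part of the between-unit variance, lower where units are unequal or one service supplies all patients. The ICCs and the even split are assumptions, not figures from the protocol. The change should be made, but the validity of the parent trial does not depend on it.

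**What to change.** In 4.5a and 4.5b:

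1. Estimate each between-arm difference with service as a fixed effect. This guards against an unequal service mix but does not deal with unit variation within a service. Do not rely on a random intercept for that, since four units cannot estimate the variance.
2. Beside each simple interval, report a sensitivity interval multiplied by √(1 + (m − 1) × ICC) at within-service ICC 0.01, 0.02 and 0.05, with m the size-weighted mean number of patients per unit (sum of squared unit sizes divided by the arm total).
3. Label the stated lengths as assuming independent patients and add the inflated values; for total sleep time at m = 25, these are 60, 66 and 80 min.
4. State that the simple intervals and t-tests are descriptive and conditional on these units, and that widening an interval does not remove the confounding of unit with arm.

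The cost is SAP wording, a service term and one extra results column. The stated precision becomes less favourable. No further patients or data are needed.

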#### 1.2 Secondary Objectives:

- a. Assess the impact of our sleep enhancement intervention on acute care utilization e.g. length of stay, 30-day readmissions
- b. Assess the implementation and feasibility of wearable digital vital signs capture in an inpatient oncologic setting using validated instruments such as system usability scale (SUS) and Weiner implementation outcomes (AIM, FIM, IAM).
- c. Assess the impact, via validated survey instruments, of our sleep enhancement intervention on patient mood, patient activation and satisfaction with inpatient stay experience.

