#### **Hypothesis**

We hypothesize that the implementation of our wearable technology intervention will result in a reduced LOS, lower 30-day readmission rates, and improved patient recovery (sleep quality and quantity), and enhanced subjective measures of patient engagement (PAM-13), satisfaction (HCAHPS) and well-being (EQ-5D-5L).

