#### 3.4 Study Design

This is a pragmatic, quasi-experimental study wherein patients admitted for any of the aforementioned conditions will be allocated into treatment (ViSi mobile plus PROSPER) and control (PROSPER only) based on non-critical care bed availability on a floor unit. Specifically, for patients on colorectal service admitted to P10 floor, one side ("unit A") will be designated as an intervention arm while the other ("unit B") will serve as a control arm. For patients admitted to Hospitalist Medicine service; patients on " unit G21" will be designated as the intervention arm, and patients admitted to "unit G22" as the control arm. Our pseudorandomization scheme is based on the naturally occurring random variation in bed assignment by availability across both the intervention and control units on a given floor, or floors at the time of patient enrollment. Since bed designation is made by hospital admissions based on availability, it is independent of the care delivery processes across the study floors / units. Our approach is intended to reduce the

burden on frontline staff, i.e., changing existing workflows to randomize patients and track allocation in a database. It also serves to reinforce the embedded intent of our QI work. Participants, family members and clinicians will not be blinded to the intervention, and given our pragmatic design, we will not attempt to control patients' communication or information-seeking behaviors beyond the pseudo-randomization described above. The intervention wing will employ the following initiatives to improve the sleep quality, level of engagement, and overall care journey of patients.

1. Passive digital monitoring of vital signs – Blood pressure, heart rate, respiratory rate, oxygen saturation, and temperature – will be wirelessly and passively collected using a U.S. Food and Drug Administration-approved wireless technology, which is worn on the wrist and chest (ViSiMobile, Sotera, San Diego, Calif), and recorded data will be sent directly to the electronic medical record (Epic Systems Corporation, Verona,Wis) at protocolized set intervals. Abnormal vitals will trigger a nursing alert via text message or page. If an in-person assessment is warranted, handheld red-spectrum lighting will be used by nursing staff as an alternative to the standard overhead white lighting.

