#### 3.8 Data collection

This will entail a blend of Epic medical record abstraction and primary data collection using validated surveys. Example of variables to be exstracted from the medical record include patient demographics (e.g., age, sex, race), primary diagnosis (cancer type), body mass index (BMI), timing of AM phlebotomy, comorbid conditions (used to compute Charlson co-morbidity index), length of stay, and 30-day readmission. To reduce survey burden for patients and ensure parity in scope of responses across the 2 groups, the majority of questionnaires will be distributed at two time points - at admission and within 24 hours of the date of discharge. All validated surveys will be administered via the hospital-owned iPad device, via text message or email, or recorded manually. A password-protected database will be used to collate the clinical and outcomes data collected. Lastly, all patients will receive a phone call 24 hours after discharge to ensure all questions are answered and follow-up care has been arranged.

2022-0190 v.23Mar2023 Page **4** of **18** 

The digital device is worn on the wrist, like a watch, and provides continuous vital sign monitoring using a three-lead system that included electrocardiography (ECG), pulse oximetry, continuous noninvasive blood pressure, mean arterial pressure, temperature, respiratory rate, heart rate, and pulse rate. Patients will be able to view their vital signs on the wrist-worn device's display screen.

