#### Additional Outcomes:

- a. Acute care utilization: Median length of stay (LOS) in hours, all-cause Emergency Room (ER) visit, and hospital readmission within 30 days postoperatively
- b. Implementation and feasibility outcomes: We will also perform psychometric assessments, from the perspective of patient and nursing stakeholders, of the implementation process and perceived effectiveness associated with our passive vital sign monitoring intervention. Three 5-item validated implementation metrics of Acceptability (AIM), Appropriateness (IAM), Feasibility (FIM) will be used to monitor and evaluate the adoption of our passive vital signs monitoring intervention. We will also leverage the system usability scale (SUS) to examine the usability and ergonomics of the passive vital sign monitoring platform (Table 3).

Outcome	Instrument	Duration	Analysis level	Assessment Calendar
Intervention	System Usability Scale	5 mins	Patient, Nurse	Admit, discharge +/- 1
usability				day
Intervention	Acceptability of Intervention	3 min	Patient, Nurse	Admit, discharge +/- 1
acceptance	measure (AIM)			day
Intervention	Feasibility of Intervention	2-5 min	Patient, Nurse	Admit, discharge +/- 1
feasibility	Measure (FIM)			day
Intervention	Intervention Appropriateness	2-5 min	Provider,	Admit, discharge +/- 1
appropriateness	Measure (IAM)		Nurse	day

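### Sub-study section 4.5a uses realised length of stay to look for confounding, but a shift after that adjustment cannot by itself distinguish confounding from a device effect on length of stay

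*Combined protocol and SAP*

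**What the plan says.** The sub-study's main analysis (section 4.5a) is the between-group difference in each actigraphy measure with a two-sided 95% confidence interval, from 50 patients per arm. Exploratory ANCOVA models follow, with "covariates of baseline measures and length of stay to assess the relative efficiency gain of each covariate, as well as potential for confounding". Baseline measures and LOS are given the same two jobs.

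Elsewhere LOS is something the device is meant to change:

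- The Hypothesis section expects that "our wearable technology intervention will result in a reduced LOS".
- Section 1.2 sets the objective "Assess the impact of our sleep enhancement intervention on acute care utilization e.g. length of stay, 30-day readmissions".
- Section 3.9, Additional Outcomes, lists "Median length of stay (LOS) in hours".

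Patients are "allocated into treatment (ViSi mobile plus PROSPER) and control (PROSPER only) based on non-critical care bed availability on a floor unit" (section 3.4) and approached within 1-2 days of admission (section 3.5), so LOS is settled after allocation and, in the device arm, after exposure. Section 4.4d averages the sleep measures over the hospitalization. Nothing in the documents replaces realised LOS with an anticipated value fixed at admission, or describes the LOS-adjusted model as a mediation analysis.

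**The concern.** A variable used to look for confounding must not be a consequence of the allocation being studied. LOS may be one here, on the trial's own hypothesis. If the device shortens stays, the arms will differ in LOS even when they were identical at admission, and adjusting for LOS will move the sleep estimate. Section 4.5a would invite the reader to take that movement as a sign of confounding.

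The efficiency comparison has a related weakness. Precision credited to a covariate that the device may change can come with a change in what is being estimated.

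The pilot does need a sound check, because allocation is not randomised. Section 3.7 says room assignment depends on unit census "as well as other clinical factors: e.g., need for an isolation room, nursing availability". The unadjusted difference may therefore be confounded, and the tool chosen to look for that should be able to show it.

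**Working it through.** **1. What a shift measures.** In a linear model with arm and one covariate, the following holds exactly:

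adjusted difference − unadjusted difference = −b × d,

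where b is the within-arm slope of sleep on LOS and d is the arm difference in mean LOS (device minus control). The origin of d does not enter. Sicker patients placed on one unit (confounding) and a device that shortens stays (no confounding) give the same shift for the same b and d.

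**2. The plan's own figures.** Section 4.5a gives an expected interval length of at most 54 min for total sleep time, so the half-width is 54/2 = 27 min. No SD is stated, so the length cannot be reproduced, only inverted:

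SD = 54 / (2 × 1.984 × √(2/50)) = 68.0 min.

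In the same way, 17 min (awakenings after sleep onset) implies 21.4 min, and 5% (sleep efficiency) implies 6.3 points. Because the lengths are upper limits, so are these SDs.

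**3. Assumed inputs, none from the documents unless noted.**
- Comparable arms and a 10% device cut in the stay after enrolment.
- Enrolment at night 1 or 2 (section 3.5 gives 1-2 days).
- Lognormal stays, median 4 or 6 nights and log-SD 0.5 or 0.7 before truncation.
- Only stays over 3 nights kept, reflecting the 3-night eligibility minimum.
- Absolute correlation r between log LOS and sleep of 0.2 or 0.4.

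**4. Size.** With s the overall SD of log LOS among eligible patients, both arms together,

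shift = r × 68.0 × |d| / s, with d now on the log scale.

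Integrating the truncated distribution gives these extremes:
- Smallest (median 6, log-SD 0.7, enrolment night 2, r 0.2): |d| = 0.0714, s = 0.548, so 0.2 × 68.0 × 0.0714/0.548 = 1.8 min, or 1.8/27 = 7% of the half-width.
- Largest (median 4, log-SD 0.5, enrolment night 1, r 0.4): |d| = 0.0824, s = 0.355, so 0.4 × 68.0 × 0.0824/0.355 = 6.3 min, or 6.3/27 = 23%.

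Sensitivity: without the 3-night floor, 1.4 to 4.6 min. With the floor and a 5% cut, 0.9 to 3.1 min. If the device does not change LOS, d = 0 and the shift is zero. Scaling by the SDs in step 2 gives 0.6 to 2.0 min for awakenings after sleep onset (× 21.4/68.0) and 0.2 to 0.6 points for efficiency (× 6.3/68.0). The adjusted difference is lower if longer stays go with less sleep, and higher if they go with more.

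**5. The same shift under two unconfounded mechanisms.**
- Sleep follows the realised stay. The unadjusted difference is a real effect acting through LOS, and adjustment removes it.
- Sleep follows only the stay the patient would have had without the device, and the device does nothing to sleep. The unadjusted difference is about 0, and adjustment creates one of about 1.8 to 6.4 min (simulated).

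**6. What one pilot would show.** In 2,000 simulated pilots of 50 per arm, in each of six combinations of these inputs, the mean shift was 1.9 to 6.3 min and its SD 3.3 to 5.8 min. A single observed shift could not identify its source.

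**7. Observation window.** Because sleep is averaged over the stay, LOS decides how many nights, and which ones, enter each patient's average. A linear LOS term does not put patients on the same nights, and it brings in the problem in step 1. It is not a clean remedy for unequal windows either.

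**The case against.** The best defence has four parts.

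- **The model is exploratory in a 100-patient pilot.** No test, decision or sample size rests on it, and the artefact is generally of the order of its own sampling noise or smaller. This stands and sets the severity.
- **LOS carries information about severity and planned procedure.** This stands in part. A shift is ambiguous rather than empty, and with no device effect on LOS the artefact vanishes. But realised LOS mixes prior severity with any device effect, and the plan has no means of separating them. Section 3.8 already collects cleaner measures of prior status: "primary diagnosis (cancer type), body mass index (BMI), timing of AM phlebotomy, comorbid conditions (used to compute Charlson co-morbidity index".
- **LOS may be there because stays differ in length.** This is a fair reason to want something in the model, although 4.5a does not give it. It argues for handling the nights directly, and any repair should do so.
- **Precision is worth having.** True, but the gain is small under the assumed correlations, and it comes from a variable that the device may change.

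A reader might also infer that 4.5a breaches the parent plan, which specifies "Inverse probability weighting using propensity scores modeled from baseline covariates". Section 3.10 governs the parent outcomes and does not bind the sub-study. It shows only that the same protocol uses baseline variables for this purpose elsewhere.

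**Conclusion.** Wrong as written, and minor. Section 4.5a assigns a confounding check to a variable that the protocol itself treats as a possible effect of the device. The conclusion rests on the passages and the identity in step 1, not on the simulated figures. Those indicate scale only: roughly 2 to 6 minutes of total sleep time against a 27-minute half-width, under assumed LOS and correlation values, and nothing if LOS is unaffected.

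Two stronger readings are tempting. One is that the sub-study's sleep result or the parent EQ-5D result is compromised. It is not: the main sub-study estimate does not adjust for LOS, and the parent EQ-5D analysis does not use this model. The other is that LOS adjustment must bias the estimate in a known direction. The documents give neither the sign of the LOS-sleep relation nor any evidence that the device will in fact change LOS in these patients.

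**What to change.** In section 4.5a, remove LOS from the ANCOVA used for confounding and efficiency. Use only variables known by enrolment that the plan already collects, few enough for 100 patients: for example service (colorectal or hospitalist), age, Charlson index and the enrolment PROMIS scores. The plan should also say what the baseline measures are. The actigraph is first placed at sub-study enrolment, and no pre-device actigraphy is described.

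Analyse LOS as an outcome. As a sensitivity analysis for unequal stays, use the nightly actigraphy in a common early window or a nightly repeated-measures model. If an LOS-adjusted model is kept, label it descriptive: neither a total effect nor a confounding check.

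Cost: a short text change, no new data and a little more analysis. Any precision from LOS is lost in one exploratory model. Under the assumptions above the mean half-width is about 26.9 min without LOS, against 26.6 with it at correlation 0.2 (26.9/26.6, about 1% wider) and 24.9 at correlation 0.4 (26.9/24.9, about 8% wider).
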